14.6 Local Provider Care Data

Table 41:Primary Care Physician Viral Load Treatment Thresholds, by Intervention Group,
Transplant Site and Perceived Ease of Access to Blood Draw Facility

		BS =X)		OC =X)	All Randomized (N=X)		
Variable Category	Num. Treated Part.	Treatment Threshold (IU/mL)	Num. Treated Part.	Treatment Threshold (IU/mL)	Num. Treated Part.	Treatment Threshold (IU/mL)	
	n	Mean (SD)	n	Mean (SD)	n	Mean (SD)	
Transplant Site							
Fred Hutchinson Cancer Research Center	XXX	xx.x (xx.x)	XXX	xx.x (xx.x)	XXX	xx.x (xx.x)	
Memorial Sloan Kettering Cancer Center	XXX	xx.x (xx.x)	XXX	xx.x (xx.x)	XXX	xx.x (xx.x)	
University of Minnesota	XXX	xx.x (xx.x)	XXX	xx.x (xx.x)	XXX	xx.x (xx.x)	
MD Anderson Cancer Center	XXX	xx.x (xx.x)	XXX	xx.x (xx.x)	XXX	xx.x (xx.x)	
Perceived Ease of Access to Blood Draw Facility							
Easy	XXX	xx.x (xx.x)	XXX	xx.x (xx.x)	XXX	xx.x (xx.x)	
Difficult	XXX	xx.x (xx.x)	XXX	xx.x (xx.x)	XXX	xx.x (xx.x)	
Overall	XXX	xx.x (xx.x)	XXX	xx.x (xx.x)	XXX	xx.x (xx.x)	
N=Number of participants in the Safety Population							

Table 42:Least-Frequent Clinician-Recommended Monitoring Interval Categories by 90 Days Post-HCT, by Intervention Group and
Stratification Variables

[Implementation note: Within each variable and category, the percentages should be row percentages within each intervention group.]

					Transpl	lant Site	Pe			s to Blood sity of Min		lity			
	Least-Frequent Clinician- Recommended Monitoring	Cancer	itchinson Research nter	Ketterin	ial Sloan g Cancer nter		rsity of esota ^a		nderson [.] Center	Ea	ısy	Diff	ïcult	Ove	erall
Treatment Arm	Interval	n	%	n	%	n	%	n	%	n	%	n	%	n	%
DBS $(N = X)$	No Further Monitoring Required	XXX	xx.x	xxx	xx.x	xxx	xx.x	xxx	xx.x	xxx	xx.x	xxx	xx.x	xxx	xx.x
	Weekly	XXX	XX.X	xxx	XX.X	xxx	XX.X	xxx	XX.X	xxx	XX.X	xxx	XX.X	XXX	XX.X
	Bi-Weekly	xxx	xx.x	xxx	xx.x	xxx	xx.x	xxx	xx.x	xxx	xx.x	xxx	xx.x	XXX	xx.x
	Monthly	xxx	xx.x	xxx	XX.X	xxx	xx.x	xxx	XX.X	xxx	XX.X	xxx	xx.x	XXX	xx.x
	Quarterly	XXX	xx.x	xxx	XX.X	xxx	xx.x	xxx	XX.X	xxx	XX.X	xxx	XX.X	XXX	XX.X
SOC (N = X)	No Further Monitoring Required	XXX	xx.x	XXX	XX.X	XXX	XX.X	XXX	XX.X	XXX	XX.X	XXX	XX.X	xxx	XX.X
	Weekly	XXX	XX.X	xxx	XX.X	xxx	xx.x	xxx	XX.X	xxx	XX.X	xxx	XX.X	XXX	XX.X
	Bi-Weekly	XXX	XX.X	xxx	XX.X	xxx	XX.X	xxx	XX.X	xxx	XX.X	xxx	XX.X	xxx	XX.X
	Monthly	XXX	XX.X	xxx	XX.X	xxx	XX.X	xxx	XX.X	xxx	XX.X	xxx	XX.X	xxx	XX.X
	Quarterly	XXX	XX.X	xxx	XX.X	xxx	xx.x	xxx	XX.X	xxx	XX.X	xxx	XX.X	XXX	XX.X
All Randomized (N = X)	No Further Monitoring Required	XXX	XX.X	xxx	xx.x	xxx	xx.x	xxx	xx.x	xxx	xx.x	xxx	xx.x	xxx	xx.x
	Weekly	XXX	XX.X	xxx	XX.X	xxx	xx.x	xxx	XX.X	xxx	XX.X	xxx	XX.X	xxx	XX.X

	Least-Frequent Clinician- Recommended Monitoring Interval	Transplant Site										se of Access ing Univers			ity
Treatment Arm		Clinician- Recommended Cancer Research Center							MD Anderson Cancer Center		isy	Difficult		Ove	erall
		n	%	n	%	n	%	n	%	n	%	n	%	n	%
	Bi-Weekly	xxx	xx.x	xxx	xx.x	xxx	xx.x	XXX	xx.x	XXX	xx.x	xxx	xx.x	xxx	xx.x
	Monthly	xxx	xx.x	xxx	xx.x	xxx	xx.x	XXX	xx.x	XXX	xx.x	xxx	xx.x	xxx	xx.x
	Quarterly	xxx	XX.X	xxx	XX.X	XXX	XX.X	XXX	XX.X	XXX	XX.X	XXX	xx.x	xxx	XX.X

N=Number of participants in the ITT Population with recommended in-office CMV monitoring intervals recorded.

n = Number of participants with results reported for the clinician-recommended CMV monitoring intervals, excluding monitoring intervals of "Other".

^aThe University of Minnesota entered the actual number of clinician-recommended CMV monitoring tests instead of the expected number of clinician-recommended CMV monitoring tests.

Tables with similar format:

[figure not shown]
- Table 43:Least Frequent Clinician-Recommended Interval Categories by 180 Days Post-HCT, by Intervention Group and Stratification
Variables
- Table 44:Least Frequent Clinician-Recommended Interval Categories by 270 Days Post HCT, by Intervention Group and Stratification
Variables
- Table 45:Least Frequent Clinician-Recommended Interval Categories by 365 Days Post-HCT, by Intervention Group and Stratification
Variables

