3.2.3. Exploratory Outcome Measures

- 1. Mean time from scheduled pick-up at participant residence (DBS tests) or blood draw facility (plasma sample) to arrival at the laboratory (hours) at all applicable test points throughout the study period
- 2. Number of mobile technology failures, sample collection failures, sample delivery failures, and sample viability failures.
- 3. Sensitivity, specificity and predictive values of CMV detection in DBS versus plasma testing
- 4. Number and type of key transplant characteristics in randomized participants and observational participants
- 5. Describe the baseline participant demographics of randomized cohort and observational cohort.
- 6. Number of participants with end-organ CMV disease (possible and proven/possible) at 1 year after HCT in randomized participants and observational participants
- 7. Describe local provider CMV treatment viral load treatment thresholds
- 8. Describe local provider CMV monitoring interval recommendations
- 9. Report composite scores of different variables of participant and provider satisfactions according to the 5-point Likert scale questionnaires.

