14. LOCAL PROVIDER CARE EVALUATION

The number of participants in each intervention group receiving pre-emptive therapy for CMV disease, as well as the mean and standard deviation of viral load at time of the decision to initiate pre-emptive therapy, by transplant site and participants' perceived ease of access to blood draw facility, as well as overall, will be summarized (Table 41).

At each quarterly contact, the least-frequent clinician-recommended monitoring interval recorded for each participant up until 90 days post-HCT (first contact), 180 days post-HCT (second contact), 270 days post-HCT (third contact) and 365 days post-HCT (final contact) will be categorized as described in Section 3.3.7.

The number and proportion of participants in each of the groups between enrollment and the first, second, third and final contacts will be summarized by intervention group, as well as by stratification variables and overall (Table 42, Table 43, Table 44, and Table 45). Note that University of Minnesota results will be excluded from the perceived ease of access stratification as this site recorded actual number of clinician-recommended CMV monitoring tests completed instead of the clinician-recommended CMV monitoring intervals.

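### The note for SAP Tables 42 to 45 asks for row percentages, but in the printed layout the proportions that Section 14 wants are column percentages

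*SAP*

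**What the plan says.** The relevant outcome is the eighth exploratory measure in SAP 3.2.3: "Describe local provider CMV monitoring interval recommendations". Section 14 turns it into Tables 42 to 45, one for each contact up to day 365. It specifies the content as follows: "The number and proportion of participants in each of the groups between enrollment and the first, second, third and final contacts", split by intervention group, by stratification variable and overall.

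The Table 42 shell (SAP Appendix 1, Local Provider Care Data) has five interval rows, from "No Further Monitoring Required" to quarterly, repeated for DBS, SOC and All Randomized. Its columns are the four sites, the Easy and Difficult strata, and Overall, each with n and %. The programming note above the shell reads: "Within each variable and category, the percentages should be row percentages within each intervention group". Tables 43 to 45 are listed under "Tables with similar format", so they inherit the layout.

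One footnote defines the arm size: "N=Number of participants in the ITT Population with recommended in-office CMV monitoring intervals recorded". Another defines n so as to leave out 'Other' intervals, in line with SAP 3.3.7. No footnote gives a denominator for the percentage columns.

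**The concern.** A row percentage is a cell divided by its row total. Here a row is one interval category in one arm, so the row total is everyone in that arm with that interval. The percentage answers the question: of those told to test weekly, what share came from this site? Section 14 asks the reverse: of this site's participants, what share were told to test weekly? In this layout that is a column percentage.

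At stake is the readability of the planned tabulation of interval recommendations. A reader who takes the percentages at face value would learn mostly how many participants each site enrolled. That reader would also find the same 100% in the Overall column of both arms.

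**Working it through.** The documents print no figure for these tables, so there is none to reproduce. The check fills the shell under both denominators.

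**Inputs from the SAP.** Rows are interval categories k within an arm. Columns are sites s, ease strata and Overall. The percentage rule is the note on Table 42.

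**Inputs assumed for illustration.** A DBS arm of 100 with site sizes 40, 30, 10 and 20, and two interval distributions, A and B. Overall is taken to contain all four sites.

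**Formulas, within one arm.**

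- Row % = 100 × n(s,k) / Σ over sites of n(s,k). For Overall the numerator is the row total itself, so the result is 100 whenever the row has anyone in it, and 0/0 when it does not.
- Column % = 100 × n(s,k) / Σ over intervals of n(s,k). For Overall it is 100 × (row total) / (all categorised participants in the arm).

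**Weekly row.**

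| Scenario | n by site | Row % by site | Row % Overall | Column % by site | Column % Overall |
|---|---|---|---|---|---|
| A | 20, 15, 5, 10 (total 50) | 40, 30, 10, 20 | 50/50 = 100 | 50 at every site | 50/100 = 50 |
| B | 36, 27, 9, 18 (total 90) | 40, 30, 10, 20 | 90/90 = 100 | 90 at every site | 90/100 = 90 |

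The row percentages are identical in A and B and equal the site sizes. The column percentages separate the scenarios.

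**Overall column, all five rows** (no further monitoring, weekly, bi-weekly, monthly, quarterly).

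- Column %: A gives 10, 50, 20, 15, 5; B gives 1, 90, 6, 3, 0. Each set sums to 100.
- Row %: A gives 100 in all five rows. B gives 100 in four rows and is undefined in the empty quarterly row.

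**Two sites.** If one site recommends weekly testing to 10 of 40 (25%) and another to 10 of 20 (50%), both counts are 10 over the same row total. Their row percentages are therefore equal despite the two-fold difference.

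**Two arms.** If 80% of one arm and 40% of the other are on weekly testing, Overall Weekly still prints 100% in both.

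**What depends on the assumptions.** The particular site percentages do. The 100% result needs only that the Overall count is the row total. If Overall were meant to leave out the University of Minnesota while the divisor kept it (the assumed site of 10), Overall Weekly in A would be 45/50 = 90%. That too describes the site mix.

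**The case against.** The strongest reply is that the note does not plainly tell the programmer to divide across sites. It opens by confining percentages to each variable and category. In neighbouring Table 41 the stub headed 'Variable Category' holds exactly the sites and ease strata. On that usage the note already points to a denominator inside each site or stratum, and the word 'row' may survive from a transposed shell. The history is inference, but the reading is plausible, and Section 14 states the intended quantity correctly. It does not rescue the note: in the layout as printed, a within-site denominator is a column percentage, so the note says two incompatible things and still has to be reworded.

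The objection also limits the consequences, and here it stands.

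- A reader might infer that these tables are the only place to see whether recommendations, which form the primary endpoint's denominator, differ between arms. The SAP does not support that. Tables 14 to 19 print the median and range of recommended tests per participant by arm, and Listing 13 lists each participant's intervals. Those outputs do not give the proportion in each interval category, but they do show the denominator by arm.
- A reader might infer that the percentages could show no difference at all. That goes too far. In scenario A the monthly row (6, 4, 2, 3) gives 40, 26.7, 13.3 and 20%, unlike the weekly row, so a contrast between sites can surface. What is lost is the level at each site and the comparison of arms.
- No information disappears. Summing n down a column recovers the denominator: for the first site in A, 4 + 20 + 8 + 6 + 2 = 40, and 20/40 = 50%.

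**Conclusion.** The note is wrong for the printed layout and conflicts with SAP Section 14. Followed literally, it would put the wrong kind of percentage in every site, ease and Overall cell of four planned tables, with 100% in each non-empty Overall cell.

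The effect is small in scope. The tables are descriptive, they serve one exploratory outcome, and no estimate, test, analysis population or primary result changes. It deserves correcting before the tables are programmed because the instruction is explicit and no footnote overrides it. It gives no reason to doubt the primary analysis.

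The conclusion rests on the ordinary meaning of a row percentage and on the shell's orientation as printed. It does not rest on the assumed counts.

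**What to change.** Replace the note with an instruction to use column percentages within each intervention group. The denominator should be the participants in that arm, and in that site, ease stratum or Overall, who have a categorised interval by that contact.

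'Having any interval recorded' will not serve as the denominator. SAP 3.3.7 and the Table 42 footnote keep 'Other' out of the categories, so a participant with only 'Other' would be counted below the line and appear in no row. Either exclude such participants from the denominator or add an 'Other' row. The categories then sum to 100% down each column.

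State the denominator in a footnote, together with whether Overall includes the University of Minnesota. Section 14 removes that site from the ease columns because it recorded tests done rather than recommended intervals. Apply the same text to Tables 42 to 45. Transposing the shell, so that intervals become columns, would also reconcile the note with Section 14, but the denominator footnote is needed either way.

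The cost is a reworded note, one footnote and the denominator in one table program. No new data are needed.

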9.1 Overall Study Design and Plan Description

[figure not shown]
Figure 1: Study Schedule

[figure not shown]
¹Quarterly contacts will be scheduled from the date of transplant, not based on the date of enrollment.

[figure not shown]
10.1 Disposition of Participants

Figure 2: CONSORT Flow Diagram

14.3.1.1 Solicited Adverse Events

[figure not shown]

Figure 4: Cumulative Incidence of CMV Disease in All Enrolled Participants, by Intervention Group

14.6 Testing and Technology Data

Figure 5: Association Between Confirmatory Whole Blood Test Results and Confirmatory DBS Test Results

[Implementation note: 1. plot the scatter plot, add Lin's Concordance correlation coefficient instead of R^2.

- 2. the x-axis should be "Confirmatory DBS Result (IU/mL)"
- 3. the data will be plot in log10 scale]

Concordance Population N Samples = XXX

[figure not shown]
[figure not shown]

Figure 6: Differences Between Confirmatory Whole Blood Test Results and Confirmatory DBS Test Results

[Implementation note: 1. Bland-Altman plot of differences if plotted here

- 1. The x-axis should be "Average of the test results (IU/mL)"
- 2. The data will be plot in log10 scale]

16.1.6 Listing of Participants Receiving Investigational Product

(not included in SAP, but this is a placeholder for the CSR)

16.2 Database Listings by Participant

16.2.1 Discontinued Participants

Listing 1: 16.2.1 Early Terminations

[Implementation Note: In the "Reason" column, concatenate any "specify" fields, including AE number and DV number. In the CSR, Participant ID should be USUBJID (not PATID) for purposes of de-identification. Sort order: Intervention Group, Participant ID.]

Intervention group	Participant ID	Reason for Early Termination	Study Day	Consent to Data Collection from Medical Records?
[e.g. DBS, SOC, Observational]				Yes/No

16.2.2 Protocol Deviations

Listing 2: 16.2.2.1: Participant-Specific Protocol Deviations

[Implementation Note: Deviations will be classified as either major or minor by the Sponsor. In the "Deviation" column, concatenate any and all "specify" fields (including visit number, etc.). If "Reason for Deviation" is "Other," concatenate "specify" field, separate by a colon, e.g., "Other: Participant refusal." If Intervention group is SOC or Observational, then the "Deviation Affected Kit Stability" column has "N/A". In the CSR, Participant ID should be USUBJID (not PATID) for purposes of de-identification. Sort order: Intervention group, Participant ID, DV Number.]

Study Group	Participant ID	DV Number	Deviation	Deviation Category	Study Day	Reason for Deviation	Deviation Resulted in AE?	Deviation Resulted in Participant Termination?	Deviation Affected Kit Stability?	Deviation Classification	Deviation Resolution	Comments
[e.g. DBS, SOC, Observational]												

Listing 3: 16.2.2.2: Non-Participant-Specific Protocol Deviations

[Implementation Note: In the "Deviation" column, concatenate any and all "specify" fields (including visit number, etc.). If "Reason for Deviation" is "Other," concatenate "specify" field, separate by a colon, e.g., "Other: Subject refusal." Sort order: Site, Start Date.]

Si	ite	Start Date	Deviation	End Date	Reason for Deviation	Deviation Resulted in Participant Termination?	Deviation Affected Kit Stability?	Deviation Category	Deviation Classification	Deviation Resolution	Comments

16.2.3 Participants and Samples Excluded from the Analysis Populations

Listing 4: 16.2.3.1: Participants Excluded from Analysis Populations

[Implementation Note: This data in this listing should be congruent with the "Participant Analysis Populations by Intervention Group" table. The reasons included here should match the SAP text that describes who will be excluded from analyses. In the CSR, Participant ID should be USUBJID (not PATID) for purposes of de-identification. Sort order: Intervention Group, Participant ID.]

Intervention Group	Participant ID	Analyses in which Participant is Included	Analyses from which Participant is Excluded	Results Available?	Reason Participant Excluded
[e.g. DBS, SOC]		[e.g., Safety, ITT, mITT,completer]	[e.g., Safety, ITT, mITT, completer, Day x]		
"Yes" in the "Results avail	able" column indicates	s that available data were removed fro	m the analysis. "No" indicates that no da	ata were available for inclusion in the	analysis.

Listing 5: 16.2.4 Demographic Data

[Implementation Note: If a participant is multi-racial, in "Race" column, note "Multiple: (list races, separated by a comma)."

In the CSR, Participant ID should be USUBJID (not PATID) for purposes of de-identification.] Sort order: Intervention Group, Participant ID.]

Intervention Group	Participant ID	Sex	Age at Enrollment (years)	Ethnicity	Race

16.2.5 Transplant, CMV Disease and Graft-Versus Host Disease Data

Listing 6: 16.2.5.1Transplant Information

[Implementation Note: In the CSR, Participant ID should be USUBJID (not PATID) for purposes of de-identification. Sort order: Intervention Group, Participant ID.]

Intervention Group	Participant ID	Donor Source	Cell Source	Conditioning Regimen	HLA match	Neoplastic Disease Status	Study Day Most Recent Chemotherapy
[e.g. DBS, SOC, Observational]		[e.g. Related, Unrelated]	[e.g. Marrow, PBSC, Cord blood]	[e.g. Myeloablative, Non- myeloablative, Reduced intensity]		[e.g. Complete remission, Subsequent remission, Partial remission, Refractory, Relapse, Newly Diagnosed, Other: [SPECIFY]]	

Listing 7: 16.2.5.2: Graft-Versus Host Disease

[Implementation Note: In the CSR, Participant ID should be USUBJID (not PATID) for purposes of de-identification. Listing should be sorted by Intervention Group, Participant ID, Visit, Disease Site, Category, and Date of Onset. At each visit, if record is for the primary site of the GVHD, then Disease Site Category is "Primary". Disease Site Category is "Secondary" for all additional instance of GVHD at additional sites reported for the visit. If "Other" cause of death indicated, include in CSR as "Other: [Cause Specified]" where Cause Specified is the information entered in the "If Other, specify" field.]

Interventio Group	n Participant ID	Visit	Disease Site Category	Study Day of Onset	Days from Transplantation	Disease Site	Maximum Grade
DBS		[e.g. Enrollment, Week 13, Week 26, Week 39, Week 52]	[e.g. Primary, Secondary]		XXX	[e.g. Gastrointestinal tract, Skin, Liver, Other: [SPECIFY]]	[e.g. Grade I, Grade II, Grade III, Grade IV, Unknown]

Listing 8: 16.2.5.3: CMV Disease Information

[Implementation Note: In the CSR, Participant ID should be USUBJID (not PATID) for purposes of de-identification. Listing should be sorted by Intervention Group, Participant ID and Date of Diagnosis. If Outcome is "Recovering/resolving" then put "Recovering/Resolving" in the "Date of Resolution" column, otherwise put the date of resolution if outcome is "Recovered/Resolved". If participant is not receiving pre-emptive therapy for CMV disease, then enter "-" in the "Viral Load at Initiation of Pre-Emptive Therapy (IU/mL)" and "Date of Viral Load Measurement" columns.]

Intervention Group	Participa nt ID	Recipient CMV Status	Donor CMV Status	Study Day of Diagnosis	Proof Category	Site of Primary CMV Infection	Study Day of Resolution	Receiving Pre- Emptive Therapy	Viral Load at Initiation of Pre-Emptive Therapy (IU/mL)	Date of Viral Load Measurement
[e.g. DBS, SOC, Observational]		[e.g. Negative, Positive, Unknown]	[e.g. Negative, Positive, Unknown]		[e.g. Proven, Probable, Possible]	[e.g. Central nervous system, Gastrointestinal tract, Respiratory tract, Blood, Other: [SPECIFY]]	[e.g. 3, Recovering/Resolving]	[e.g. Yes, No]	[e.g. xxx, -]	[e.g. DDMMMYYY Y, -]

16.2.6 Individual CMV Monitoring Data

Listing 9: 16.2.6.1 Individual CMV Monitoring Data

[Implementation Note: In the CSR, Participant ID should be USUBJID (not PATID) for purposes of de-identification. Hour in date-time fields will be from the 24-hour clock. Listing should be sorted by Intervention Group, Participant ID, Collection or Test Date, and Sample Type. The order of Sample Type is DBS, Confirmatory DBS, and Confirmatory WB. Results in copy/mL will be converted to IU/mL at a rate of 4 copies per 1 IU. (Ref: https://depts.washington.edu/labweb/referencelab/clinical/TestForms/CMV_IU-ml_Conversion.pdf).

Test Result Source is "Central Laboratory Data Upload" if the result is from a sample sent to the central laboratory and entered on the Central Data Upload form. If the result was abstracted through medical chart review and entered on the CMV form, then Test Result Source is "Chart Review".]

Intervention Group	Participant ID	Study Day of Collection or Test ^a	Study Day	Test Result Source	Days from Scheduled Pick-Up to Arrival at Study Laboratory	Sample Type	Result (IU/mL)	Result Within Limits of Detection?		
[e.g. DBS, SOC]			xxx	[e.g. Central Laboratory Data Upload, Chart Review]	[e.g. xx.x, NA (if Test Result Source is Chart Review]	[e.g. DBS, Confirmatory WB, Confirmatory DBS, Plasma, Serum, Whole blood]	[e.g. xx.x, Unevaluable]	[e.g. Yes, No, Above Standard Curve, Less than 1 copy/mL, NA (if unevaluable)]		
	^a Collection or test date contains the collection date if the sample was collected using a study-provided kit and sent to the study laboratory for testing (DBS, Confirmatory WB, Confirmatory DBS). If the sample was collected as part of a participant's clinical care and the test results were obtained by medical chart review, then the column contains the test date									

Listing 10: 16.2.7 DBS Testing Reminder Listing

[Implementation Note: In the CSR, Participant ID should be USUBJID (not PATID) for purposes of de-identification. The listing should be sorted by Participant ID and Sequence Number.]

Participant ID	Enrollment (Study Day)	Expected Date of Notification	Sequence Number	Preferred Notification Method	Reminder Time	Reminder Sent?
			[e.g. 001, 002, etc.]	[e.g. Email, Text message, Both email and text message]	Day HH:MM AM/PM	Yes/No

Listing 11: 16.2.8 Listing of Shipment Information

[Implementation Note: In the CSR, Participant ID should be USUBJID (not PATID) for purposes of de-identification. The listing should be sorted by Participant ID and Sequence Number.]

Participant ID	Enrollment (Study Day)	Sequence Number	Kit Number	Sample Type	Study Day of Collection	Study Day of Scheduled Pick-Up	Study Day of Sample Received			
		[e.g. 001, 002, etc.]		[e.g. DBS, WB]						
Study Day of Collection and Scheduled Pick-Up are participant-entered data. Study Day of Sample Received is entered by the study laboratory.										

Listing 12: 16.2.9 Listing of Sample Collection Kit Problems

[Implementation Note: In the CSR, Participant ID should be USUBJID (not PATID) for purposes of de-identification. The listing should be sorted by Participant ID and Sequence Number.]

Participant ID	Enrollment (Study Day)	Kit Number	Sample Type	Study Day of Problem Reported	Description of Problem	Was Kit Used by Participant?
	XXX		[e.g. DBS, WB]	XXX	Description of problem	Yes, No

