2.1.5.2 Summary of DBS Assay Performance vs Standard Plasma PCR Clinical Assay

The performance of the current DBS PCR assay was compared to an ultrasensitive plasma PCR assay (lower level of quantitation 50 IU/mL) that is used clinically at the University of Washington Clinical Virology Laboratory to monitor patients for CMV infection. The standard used in the clinical PCR assay is the WHO International Standard for human cytomegalovirus (HCMV). Residual whole blood samples from specimens that were submitted for clinical plasma PCR testing were also examined by the DBS assay. The primary goal of the study was to determine whether the DBS assay detected CMV DNA in whole blood samples that were determined to be positive at the 1000 (3.0 log 10) IU/mL level in the clinical PCR assay, a level that is commonly used to trigger preemptive treatment of patients in the late period after hematopoietic cell transplantation (HCT). As a secondary goal, the study also examined the ability of the DBS to detect CMV DNA in whole blood samples that are positive at the 500 (3.0 log10) IU/mL level also used by some sites to start preemptive therapy.

Residual samples from patients who had plasma viral loads ≥ 150 (2.18 log₁₀) IU/mL were spotted on to filter cards (50uL). The residual blood sample was used with 24-72

[figure not shown]
hours after the sample had been drawn. A total of 145 clinical samples from 69 persons were collected and tested. From the 145 clinical samples, 22 had plasma CMV viral load \geq 1000 IU/mL; 48 had known plasma CMV viral load \geq 500 IU/mL and 97 had viral loads \leq 500 IU/mL. The results of the comparisons at two different thresholds are summarized in the table below.

Table 2. Summary of DBS assay evaluation

Clinical plasma PCR and DBS PCR results with different thresholds		
Clinical Plasma CMV PCR \geq 500 (2.7 log ₁₀) IU/mL	48/145	
Clinical plasma CMV PCR ≥500 IU/mL (2.7 log ₁₀) and DBS positive	44/145	
(Clinical PCR range: 510-36000 [2.7-4.6 log ₁₀] IU/mL)		
Clinical plasma CMV PCR <500 IU/mL (2.7 \log_{10}) and ≥ 150 (2.18 \log_{10})	97/145	
IU/mL		
Clinical plasma CMV PCR <500 IU/mL (2.7 log ₁₀) and DBS positive	59/145	
(Clinical PCR range: 41-490 [1.6-2.7 log ₁₀] IU/mL)		
Clinical plasma CMV PCR ≥1000 (3.0 log ₁₀) IU/mL	22/145	
Clinical plasma CMV PCR ≥1000 (2.7 log ₁₀) IU/mL and DBS positive	21/145	
(Clinical PCR range: 1000-36000 [3.0-4.6 log ₁₀] IU/mL)		

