APPENDIX A: DBS CMV PCR ASSAY COMPARISON

Description	Procedure in Publication	Current Procedure
Filter paper used	Whatman FTA Elute cards	Whatman 903 Protein Saver cards
Size of each punch	3 mm in diameter	6 mm in diameter
Number of punchs used for DNA extraction	4	2
PCR master mix	QuantiTect Muliplex PCR mix with ROX	QuantiTect Muliplex PCR NoROX mix
PCR Machine	7900HT sequence detection system	QuantStudio 7 flex real-time PCR system
IU conversion	1 IU= 4 copies (AcroMetrix)*	1 IU=1.4 copies (WHO)
Internal control template	Spiked into PCR master mix	Spike into extraction lysis buffer
Internal control primers and probe	EXO	EXO BS
DNA Elution volume	100 ul	100 ul
Amount of DNA used for each PCR	20 ul	20 ul
CMV primers and probe	gB and IE-EX4	gB and IE-EX4
CMV PCR standard	1e1 to 1e5	1e1 to 1e5

DMID Protocol Number 16-0098
CMV DBS Testing in HCT Recipients

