3.3.14. Unanticipated Adverse Device Effects or Device Failures

False positive results and false negative results from the testing conducted at the University of Washington Laboratory on DBS samples are Unanticipated Adverse Device Effects (UADEs) and are considered Device Failures and will be reported as an Unanticipated Problem.

The following rules will be used to identify possible false positive or false negative results:

False Positive is reported in either of the following cases:

- A DBS sample is positive at a viral load above the treatment threshold at the respective site and a confirmatory WB sample is negative and collected within 3 days of the DBS sample.
- A confirmatory DBS is positive at a viral load above the treatment threshold at the respective site and a confirmatory WB sample is negative and collected on the same day.

False Negative is reported in either of the following cases:

- A CMV PCR result identified in the quarterly chart review is positive at a viral load above the treatment threshold at the respective site and a DBS sample is negative and collected within 3 days of the clinical plasma sample.
- A confirmatory DBS sample is negative and a confirmatory WB sample is positive at a viral load above the treatment threshold at the respective site collected on the same day.

Both DBS and WB results for UADE monitoring are obtained from the laboratory data uploaded by the University of Washington Laboratory (See Section 3.3.8 and Section 3.3.9 for further details).

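### The SAP's only copies-to-IU rule uses 4 copies per IU, but Protocol Appendix A gives 1.4 for the current DBS assay, so a DBS result held in copies/mL would be listed 2.86-fold too low

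*SAP*

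**What the plan says.** **SAP Listing 9 (Appendix 3, section 16.2.6).** The implementation note reads: "Results in copy/mL will be converted to IU/mL at a rate of 4 copies per 1 IU". It cites a University of Washington conversion sheet. The listing mixes DBS, confirmatory DBS and confirmatory whole-blood (WB) results from the central laboratory with plasma, serum and whole-blood results from chart review. The note is not restricted to any of these. No other conversion rule appears in the SAP.

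**Protocol Appendix A.** The columns are headed "Description Procedure in Publication Current Procedure". The conversion row reads "IU conversion 1 IU= 4 copies (AcroMetrix)* 1 IU=1.4 copies (WHO", so 4:1 belongs to the published procedure and 1.4:1 to the current one. Protocol 6.1.2 and 8.1.2.1 name the Whatman 903 Protein Saver card, which is the card in the current column.

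**Protocol 2.1.5.2.** On the plasma comparator in the validation study: "The standard used in the clinical PCR assay is the WHO International Standard for human cytomegalovirus (HCMV".

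**SAP 3.3.14.** A false positive requires: "A DBS sample is positive at a viral load above the treatment threshold at the respective site and a confirmatory WB sample is negative". A false negative on same-day confirmatory samples requires: "A confirmatory DBS sample is negative and a confirmatory WB sample is positive at a viral load above the treatment threshold". The other false-negative rule puts the threshold on a chart-review PCR result. SAP 4.5.3 defines a true positive with the same condition on the DBS load as the false-positive rule.

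**Units in the shells.** Treatment thresholds (Table 41), the DBS result in the device-effect listing (Table 27), Lin's coefficient (Table 38) and Figures 5 and 6 are all in IU/mL.

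**The concern.** The SAP's single factor is the one the protocol assigns to the published assay, not to the assay used in this trial. Wherever the rule is applied to a current-assay DBS result, the listed value is wrong in a known direction and by a known amount.

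What is at stake beyond the listing depends on how far the conversion travels. SAP 3.3.14 treats false DBS results as unanticipated adverse device effects (UADEs), to be reported as Unanticipated Problems, and one of its two kinds of error is judged by whether the DBS load exceeds a site threshold. If understated loads fed that rule, some false positives would not be flagged. The true-positive count behind sensitivity and positive predictive value would be affected in the same way. A programmer holding copy-unit data who needs IU/mL for those outputs will find only the 4:1 rule in the SAP.

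**Working it through.** **Inputs**
- SAP factor: 4 copies per IU (Listing 9 note).
- Protocol factor for the current DBS procedure: "1 IU=1.4 copies (WHO", that is 1.4 copies per IU (Appendix A).
- Illustrative thresholds: 1000 and 500 IU/mL, which Protocol 2.1.5.2 describes as used to start preemptive therapy. They are assumed here only as examples. The trial sites' own thresholds are recorded on an eCRF and do not appear in the documents.

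**Step 1: source of the 4.** The SAP figure equals Appendix A's entry for the published procedure and differs from its entry for the current procedure.

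**Step 2: size of the understatement.** For a result of C copies/mL, the ratio of listed to current-assay value is (C/4)/(C/1.4) = 1.4/4 = 0.35. Inverted, this is 4/1.4 = 2.857-fold, and log10(2.857) = 0.456. A load of 1000 IU/mL at 1.4:1 is 1400 copies/mL and would be listed as 1400/4 = 350 IU/mL.

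**Step 3: loads that change side of a threshold T.** The copies needed to reach T are T × factor.

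| T (IU/mL) | Copies/mL at 1.4:1 | Copies/mL at 4:1 | Band that drops below T, in IU/mL at 1.4:1 |
|---|---|---|---|
| 1000 | 1400 | 4000 | 1000 to 2857 |
| 500 | 700 | 2000 | 500 to 1429 |

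**Step 4: which rules use the DBS load.** Only the false-positive rules (SAP 3.3.14) and the true-positive rules (SAP 4.5.3) do. The false-negative and true-negative rules need only a negative DBS and put the threshold on the WB or chart result. Taking negative to mean that CMV was not detected, a positive DBS pushed below the threshold fits none of the four cells, so the pair drops out. Under the SAP 4.5.3 formulas, losing true positives lowers sensitivity, losing false positives raises specificity, positive predictive value can move either way, and negative predictive value does not change.

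**Step 5: concordance.** If DBS is converted at 4:1 and WB is not, the log10 differences in Figure 6 shift by about 0.46. If both are converted by one common factor, the log10 differences and Lin's coefficient are the same whatever that factor is.

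To show the first case, assume perfect correlation, equal variances and a log10 SD of s. With d = 0.456, Lin's coefficient is 2s²/(2s² + d²): 0.71, 0.78, 0.86 and 0.91 for s = 0.5, 0.6, 0.8 and 1.0. These SDs are assumptions, not figures from the documents.

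**Step 6: what the documents leave open.** No passage gives the unit in which the central laboratory uploads DBS or WB results, and none says that the Listing 9 conversion is used in SAP 3.3.14, SAP 4.5.3, Tables 27 and 38 or Figures 5 and 6.

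**The case against.** A reader might infer that DBS loads are being compared with treatment thresholds at about a third of their value, so that device failures are being missed and the screen must be run again. The documents do not support that, for these reasons:

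- It requires DBS results to be held in copies/mL and a note attached to one listing shell to drive SAP 3.3.14. Neither is stated, and SAP 3.3.14 and 4.5.3 do not refer to the note.
- There are signs that DBS results arrive in IU. Appendix A includes IU conversion in the laboratory's own procedure, and Table 27 fixes the DBS column in IU/mL while leaving only the comparator's unit open. The note may be meant for chart-review results, to which Appendix A's 1.4 would not necessarily apply.
- The detection code in Listing 9 for results under 1 copy/mL shows that copy units were contemplated, but it is an example entry in a column covering every source.
- The conversion sheet cited in the note cannot be seen here, and it may concern a different assay.
- A concordance bias cannot be asserted outright, because it needs DBS and WB to be converted differently.
- Protocol 9.3 separately requires investigators to report false assay results within 10 working days, so the SAP screen is not the only route.

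All of this stands against the stronger reading. It does not remove the contradiction. The note covers every copy/mL result in a listing that includes current-assay DBS samples, and the protocol gives a different factor for that assay. Whatever the cited sheet says, the two documents disagree.

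**Conclusion.** The SAP's only copies-to-IU rule conflicts with the protocol's factor for the trial's own device. Any current-assay DBS result held in copies/mL would be listed 2.86-fold (0.46 log10) too low. That much follows from the two documents alone.

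The rest is conditional:
- **Threshold classification.** False positives and true positives would be under-counted if DBS results are in copies and the same conversion is used for SAP 3.3.14 and 4.5.3. At a 1000 IU/mL threshold the affected loads are 1400 to 4000 copies/mL.
- **Concordance.** A shift of about 0.46 log10 arises only if DBS is converted at 4:1 and WB is not.
- **No effect.** DBS results uploaded in IU/mL are unaffected.

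The primary adherence endpoint does not use viral load and is unaffected. DBS assay performance is an exploratory outcome. Severity is minor to moderate: the rule is wrong as written and easily corrected, but damage to the device-failure output has not been shown.

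**What to change.** 1. Reconcile the Listing 9 note with Appendix A: for current-assay DBS results held in copies/mL, convert at 1.4 copies per IU.
2. State the upload unit and the conversion factor, if any, for each source: central DBS, central WB and chart review.
3. For chart results in copies/mL, use the reporting laboratory's own factor. Where it cannot be obtained, list the result unconverted and leave it out of rules expressed in IU.
4. Move the rule from the listing note into the SAP's derived-variable definitions (section 3.3), and state that it governs SAP 3.3.14 and 4.5.3, Tables 27 and 38 and Figures 5 and 6.

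The cost is one programming constant, a sentence per source, a query to the central laboratory about its upload unit and WB factor, and a modest effort to obtain local factors. If uploads prove to be in IU/mL already, the change for central results is clarifying wording only.
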